6.1. Critical Baseline Assessments

For subjects in BEL113750: Subjects will be assessed for eligibility at the Week 48 visit of BEL113750. Only subjects who complete BEL113750 through the Week 48 visit and have a final BEL113750 disease assessment at Week 52 are eligible for this study. Written informed consent (including consent for the use and disclosure of research-related health information) must be obtained. Subjects must be able to receive the first dose of belimumab for BEL114333 four weeks (minimum of 2 weeks, maximum of 8 weeks) after the last dose in BEL113750.

For subjects in C1115: Subjects will be assessed for eligibility at the Day 168 visit of C1115. Only subjects who complete C1115 through the open-label extension phase and have a final disease assessment at Day 168 are eligible for this study. Written informed consent (including consent for the use and disclosure of research-related health information) must be obtained on or before the Day 168 visit. Subjects must be able to receive the first dose of IV belimumab (Day 0) for BEL114333 one week after the last SC dose in C1115. The EXIT visit of the C1115 study (Week 24) serves as the Day 0 visit for the Protocol BEL114333, and will have a +1 week visit window.

6.1.1. Procedures (Day 0)

6.1.1.1. Subjects in BEL113750

The Week 52 visit in BEL113750 will serve as the Day 0 visit for Protocol BEL114333. The subject must sign the informed consent for this protocol between the Week 48 and Week 52 visits of the BEL113750 study prior to any procedure in this protocol (that is not present in the BEL113750 protocol) being performed. On Day 0 of this study, a subject will be reassessed for Inclusion/Exclusion criteria of the BEL114333 study and receive belimumab, after completing the Week 52 procedures from the BEL113750 study. Site personnel will access the IVRS to enrol the subject in the study.

Procedures necessary for this protocol and for the prior Phase III protocol (BEL113750) need only be performed once. The results of any Day 0 procedure in this protocol which are also part of the BEL113750 protocol should be recorded on the BEL113750 eCRF. Only the additional procedures required for this protocol will be recorded in the BEL114333 protocol eCRF. The relevant Week 52 eCRF data will be transferred to the Day 0 BEL114333 eCRF.

The following assessments will be performed as part of the Week 52 assessment on BEL113750 and need only be performed once as described above.

- Urine for pregnancy testing- for all women with an intact uterus, unless exempted from pregnancy testing (i.e., of non-childbearing potential - women who had a hysterectomy, are post-menopausal which is defined as 1 year without menses, have both ovaries surgically removed or have current documented female sterilization procedure).
- Record of Concurrent Medications.

- Adverse Events.
- Physical exam
- Vital signs (Systolic and diastolic blood pressure (sitting), heart rate, and oral temperature will be measured. See Section 6.3.11).
- Blood samples for: (see [Appendix 5](#)– Laboratory Tests):
 - Haematology.
 - Modified Chem 20 (non-fasting). (CPK MUST be done for subjects with myositis in order to score SELENA SLEDAI/BILAG).
 - Serum Immunoglobulin isotypes (IgG, IgM, IgA).
 - Immunogenicity testing.
 - Biological markers (Complement C3 and C4)
 - Anti-dsDNA autoantibodies.
 - B-cell subsets (CD20⁺, CD20⁺/27⁺ memory, CD20⁺/27⁻ naïve, CD20⁺/69⁺ activated, CD20⁺/138⁺ plasmacytoid, CD19⁺/27^{BRIGHT}/38^{BRIGHT} SLE subset and CD20/138⁺ plasma cells) at selected sites.
- Urine sample for:
 - Routine urinalysis.
 - Spot urine for macroscopic/microscopic/proteinuria assessments.
- Disease activity scales:
 - Physician’s Global Assessment (PGA). (See [Appendix 1](#)).
 - SELENA SLEDAI (See [Appendix 1](#); refer to Section 6.2.2.3 Guidelines for Scoring Proteinuria).
 - SLE Flare Index. (See [Appendix 1](#)).
 - BILAG. (See [Appendix 2](#)).
 - SLICC/ACR Damage Index (See [Appendix 3](#)).

The following additional procedures beyond those described above are required at Day 0 for Protocol BEL114333:

- Ensure Informed Consent Form has been signed.
- Confirm Eligibility.
- PT/PTT
- Administer belimumab.

6.1.1.2. Subjects in C1115

The Day 168 visit of the open-label extension of C1115 will serve as the Day 0 visit for Protocol BEL114333. The subject must sign the informed consent for this protocol on or before the Day 168 visit of the open-label extension of C1115 prior to any procedure in this protocol (that is not present in the C1115 protocol) being performed. On Day 0 of this study, a subject will be reassessed for Inclusion/Exclusion criteria of the BEL114333 study and receive IV belimumab, after completing the Day 168 procedures from the C1115 study. Site personnel will access the IVRS to enrol the subject in the study.

Procedures necessary for this protocol and for the prior Phase III protocol (C1115) need only be performed once. The results of any Day 0 procedure in this protocol which are also part of the C1115 protocol should be recorded on the C1115 eCRF. Only the additional procedures required for this protocol will be recorded in the BEL114333 protocol eCRF.

The following assessments will be performed as part of the Day 168 assessment on C1115 and need only be performed once as described above and entered into the C1115 eCRF only.

- Urine for pregnancy testing- for all women with an intact uterus, unless exempted from pregnancy testing (i.e., of non-childbearing potential - women who had a hysterectomy, are post-menopausal which is defined as 1 year without menses, have both ovaries surgically removed or have current documented female sterilization procedure).
- Record of Concurrent Medications.
- Adverse Events.
- Blood samples for: (see [Appendix 5](#)– Laboratory Tests):
 - Haematology.
 - Modified Chem 20 (non-fasting). (CPK MUST be done for subjects with myositis in order to score SELENA SLEDAI/BILAG).
 - PT/PTT
 - Serum Immunoglobulin isotypes (IgG, IgM, IgA).
 - Immunogenicity testing.
 - Biological markers (Complement C3 and C4)
 - Anti-dsDNA autoantibodies.
 - B-cell subsets (CD20⁺, CD20⁺/27⁺ memory, CD20⁺/27⁻ naïve, CD20⁺/69⁺ activated, CD20⁺/138⁺ plasmacytoid, CD19⁺/27^{BRIGHT}/38^{BRIGHT} SLE subset and CD20⁺/138⁺ plasma cells) at selected sites.
- Urine sample for:
 - Routine urinalysis.

- Spot urine for macroscopic/microscopic/proteinuria assessments.
- Disease activity scales:
 - Physician's Global Assessment (PGA). (See [Appendix 1](#)).
 - SELENA SLEDAI (See [Appendix 1](#); refer to Section 6.2.2.3 Guidelines for Scoring Proteinuria).
 - SLE Flare Index. (See [Appendix 1](#)).
 - BILAG. (See [Appendix 2](#)).

The above Day 168 eCRF data will be transferred programmatically from the C1115 eCRF and merged with the datasets for BEL114333. This data will not be visible in the BEL114333 eCRF.

The following additional procedures beyond those described above are required at Day 0 for Protocol BEL114333:

- Ensure Informed Consent Form has been signed.
- Confirm Eligibility.
- Physical exam
- Vital signs (Systolic and diastolic blood pressure (sitting), heart rate, and oral temperature will be measured. See Section 6.3.11).
- SLICC/ACR Damage Index (See [Appendix 3](#)).
- Administer belimumab.

6.2. Efficacy

6.2.1. Efficacy Endpoints

6.2.1.1. Primary Endpoint

The primary efficacy endpoint is response rate at each scheduled visit when complete efficacy evaluations occur (e.g., Weeks 24 and 48 of Year 1 and Year 2, etc).

- A response is defined as:
 - ≥ 4 point reduction from baseline in SELENA SLEDAI score,AND
 - No worsening (increase of < 0.30 points from baseline) in Physician's Global Assessment (PGA),AND

- No new BILAG A organ domain score or 2 new BILAG B organ domain scores compared with baseline at the time of assessment (i.e., Weeks 24 and 48 of Year 1 and Year 2, etc).

6.2.1.2. Secondary Endpoints

- Percent of subjects with ≥ 4 point reduction from baseline in SELENA SLEDAI score assessed every 24 weeks.
- Number of days of daily prednisone dose ≤ 7.5 mg/day and/or reduced by 25% from baseline over time.
- Time to first severe SLE Flare Index (SFI) flares assessed over time.

NOTE: Baseline will be defined as study Day 0 of BEL113750 study or C1115 study as appropriate. Additionally, for the group of subjects who received placebo in BEL113750, a secondary analysis will be performed by defining the baseline as Day 0 of the current study the day placebo subjects in BEL113750 will have begun to receive belimumab treatment. (See Section 8.1)

6.2.1.3. Other Endpoints

Disease Activity:

- Duration of primary response assessed every 24 weeks.
- Change in Systemic Lupus International Collaborating Clinics (SLICC)/ACR Damage Index assessed every 24 weeks.
- Percent change in PGA assessed every 24 weeks.

Flares:

- For analysis, SLE Flares will be defined in 3 ways:
 - BILAG 1A/2B Flare: A new BILAG A organ domain score or 2 new BILAG B organ domain scores compared with baseline.
 - BILAG A Flare: A new BILAG A organ domain score compared with baseline.
 - SFI Flare: A mild/moderate or severe flare according to the modified SELENA SLEDAI SLE Flare Index (modified excludes severe flares from the SELENA SLEDAI flare assessment that were triggered only by an increase in SELENA SLEDAI score to >12).
- Time to first SFI flare assessed over time.
- Time to first 1A/2B BILAG flare assessed over time.
- Time to first BILAG A flare assessed over time.

Organ-specific Measures:

- Renal flare rate and time to first renal flare assessed over time.
 - A SLE renal flare is defined as the occurrence of 1 or more of the following in 2 or more consecutive visits during the study:

1. A reproducible increase in 24-hour urine protein equivalent levels to
 - a. >1 g if the baseline value was <0.2 g,
 - b. >2 g if the baseline value was 0.2 to 1 g, or
 - c. More than twice the value at baseline if the baseline value is >1 g.
 2. A reproducible increase in serum creatinine of >20% or at least 0.3 mg/dL, accompanied by proteinuria (>1 g/24 hour equivalent), haematuria (≥ 4 red blood cells [RBCs]/high-power field [hpf]), and/or RBC casts.
 3. Treatment emergent, reproducible hematuria (≥ 11 to 20 RBCs/ hpf) or a reproducible increase in hematuria by 2 grades compared with baseline, associated with >25% dysmorphic RBCs, glomerular in origin, exclusive of menses, accompanied by either an 0.8 g increase in 24-hour urinary protein levels (equivalent) or new RBC casts [[Alarcón-Segovia, 2003](#)].
- Percent change in proteinuria by visit.

Prednisone:

- Percent change from baseline of prednisone dose at each scheduled visit.
- Percent of subjects whose average prednisone dose has been reduced to ≤ 7.5 mg/day from > 7.5 mg/day at baseline over time.

Details of the analysis of other supporting endpoints will be given in the Reporting and Analysis Plan (RAP).

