Section 6.2.1.3 Other [Efficacy] Endpoints Duration of primary response [SRI] assessed every 24 weeks.	This endpoint has been removed.	Because the investigator has much more freedom in prescribing concomitant medications during the OL continuation study BEL114333, this could potentially confound evaluating the duration of the SRI response.
Section 6.2.1.3 Other [Efficacy] Endpoints	The following efficacy endpoints were added: Change and percent	Additional analyses are being reported to enable the long-term, data to be further

Protocol	Reporting & Analysis Plan	
Statistical Analysis Plan	Statistical Analysis Plan	Rationale for Changes
	change from baseline in SELENA SLEDAI. SLICC/ACR Damage Index Worsening from baseline.	evaluated.
Section 6.2.1.3 Other [Efficacy] Endpoints Renal flare rate and time to first renal flare assessed over time. A SLE renal flare is defined as the occurrence of 1 or more of the following criteria (not shown here) in 2 or more consecutive visits during the study. See RAP, Section 8.2.8, for details of the criteria.	The renal flare definition has been revised for study BEL114333, as the occurrence of one or more of the following criteria (not shown here) at a single visit in which assessments are performed.	Assessments every 6 months during study BEL114333 will not allow the use of the same definition of renal flares as in the respective parent studies, which requires assessments to be performed at 2 or more consecutive monthly visits.
Section 8.1 Data Analysis Considerations	Although the efficacy data will be tabulated by parent study randomised treatment groups, as mentioned in the protocol, the graphical displays will be shown for the total Safety population only.	The graphs align with the interpretation of response over time rather than comparisons between treatment groups.

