2.4.1. Treatment Comparisons

All subjects will be treated with open-label IV belimumab for the duration of the study BEL114333. The analyses will be performed on data from all subjects as one total belimumab treatment group by year of belimumab treatment.

As subjects started to receive belimumab treatment in the parent study, or the open-label extension of the parent study BEL112341, or the open-label study BEL114333, different time points to start of belimumab treatment will be used to define subject follow up in the analysis. See Figure 1.

Analyses will be based on all available follow-up from the first dose of belimumab treatment through to study end.

Additional safety (e.g., labs), efficacy and study population summaries will be presented by parent study randomised treatment groups (belimumab vs placebo); however, these comparisons will be descriptive in nature. For the remainder of the document, parent randomised treatment group will be used to refer to the treatment to which a subject was randomised in the parent study, irrespective of formulation.

Figure 1 First Belimumab Dose/Baseline Definition

Analyses will be based on all available data from the first belimumab dose through to study end, BEL114333. As subjects started to receive belimumab in the parent study, or the open-label extension of BEL112341, or the open-label study BEL114333, different timepoints to start of belimumab treatment are used in the analysis (as shown). Baseline is defined as the last available value prior to the first belimumab dose.

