8.2.8. Time to First Renal Flare

Only time to first renal flare will be analysed. Although a renal flare rate was of interest at the time of the protocol design writing, renal flare rates have been relatively

uncommon, and do not provide much clinical value at this current time. Focus will be placed upon providing a summary of the first renal flare event.

Assessments every 6 months during BEL114333 will not allow the use of the same definition of renal flares as in the parent studies, which requires assessments to be performed at two or more consecutive monthly visits. Thus, a renal flare is defined as the occurrence of one or more of the following criteria at a single (belimumab) visit at every Week 24 and Week 48, timepoints at which both protein creatinine ratio and lab assessments are scheduled in the protocol. Note, when identifying renal flares, data within the visit window at Week 24 and Week 48 visits will be considered.

- 1. An increase in 24-hour urine protein equivalent levels to
 - a. > 1 g if the baseline value was < 0.2 g,
 - b. > 2 g if the baseline value was 0.2 to 1 g, or
 - c. More than twice the value at the baseline if the baseline value is > 1 g.
- 2. An increase in serum creatinine of >20 % or an increase of at least 0.3 mg/dL, accompanied by at least one of proteinuria (>1 g/24 hour equivalent), hematuria (≥ 4 red blood cells [RBCs]/high-power field [hpf]), cellular (RBC or WBC) casts. The inclusion of 'at least one of' and 'RBC or WBC' casts is an addition to the protocol specified definition. This addition has been included in the parent study BEL113750 RAP.
- 3. Treatment-emergent, hematuria (≥ 11 to 20 RBCs/hpf) or an increase in hematuria by 2 grade compared with baseline, associated with > 25% dysmorphic RBCs, glomerular in origin, exclusive of menses, accompanied by either an 0.8 g increase in 24-hour urinary protein levels (equivalent) or new RBC casts [Alarcón-Segovia, 2003].

To clarify criterion 2, [an increase in serum creatinine of > 20% OR an increase of at least 0.3 mg/dL], AND [proteinuria (> 1 g/24-hour equivalent) OR hematuria (≥ 4 red blood cells {RBCs}/high-power field {hpf}) OR cellular (RBC or WBC) casts].

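### The declared move from a confirmed to a single-visit renal flare has no confirmed sensitivity analysis, although the Week 24/48 visit grid allows one

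*Protocol*

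**What the plan says.** Protocol 6.2.1.3 defines a renal flare as "the occurrence of 1 or more of the following in 2 or more consecutive visits during the study". Each criterion is also worded as a repeatable finding; the proteinuria criterion, for example, opens "A reproducible increase in 24-hour urine protein equivalent levels to". The protocol does not say that the consecutive visits are monthly.

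SAP 2.1, Table 1, lists the change openly. The flare becomes "the occurrence of one or more of the following criteria (not shown here) at a single visit in which assessments are performed". SAP 8.2.8 gives the reason: "Assessments every 6 months during BEL114333 will not allow the use of the same definition of renal flares as in the parent studies", a definition "which requires assessments to be performed at two or more consecutive monthly visits". SAP 8.2.8 restricts the visits to Week 24 and Week 48 of each year, where spot ratio and laboratory tests are both scheduled.

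The numerical thresholds stay as in the protocol, including "More than twice the value at the baseline if the baseline value is > 1 g". Criterion 2 is widened slightly by adding WBC casts. Every comparison uses one baseline value: "Baseline is defined as the last available value prior to the first belimumab dose".

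SAP 8.2.8 also drops the renal flare rate. The renal flare displays are Table 3.23 (time to first flare), Table 3.24 (subjects with at least one flare, by visit) and Figure 3.12 (cumulative incidence). None uses a confirmed definition.

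**The concern.** The SAP's reason shows that monthly confirmation is unavailable. It does not show that confirmation is unavailable. This protocol scheduled spot urine only at Day 0, Week 24, Week 48 and Exit, so its consecutive-visit rule can be applied to that schedule.

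Three features make an unconfirmed first crossing fragile here:

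- Proteinuria rests on spot ratios alone; SAP 8.2.9 notes that no subject had a 24-hour collection.
- All later values are compared with the same single baseline reading, so a low reading raises the risk at every later look.
- The endpoint is the first crossing over many looks, so false crossings accumulate with follow-up.

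At stake is what the long-term renal flare curve can support. Without a confirmed companion, a reader cannot tell how much of it is measurement noise.

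**Working it through.** The plan states no flare rate, spot-ratio variability or number of subjects with baseline above 1 g, so there is no planned figure to reproduce. The check asks how often a subject with no true change would be counted.

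**Inputs from the documents.** Proteinuria thresholds (SAP 8.2.8): above 1 g if baseline is below 0.2 g; above 2 g if baseline is 0.2 to 1 g; more than twice baseline if baseline is above 1 g. There are two looks per year. The visit map in SAP 11.2.2 allows at most 14 looks (BEL113750 belimumab), 12 (BEL113750 placebo), 10 (BEL112341 belimumab) and 8 (BEL112341 placebo).

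**Assumptions, not in the documents.** Within-subject CV of 20 to 40% for the main figures; log-normal error; constant true level; 12 looks. For the spread of true proteinuria across subjects: log-normal, median 0.15 to 0.3 g, log-SD 1.0 to 1.2.

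**One look, true level well above 1 g.** With σ = √ln(1 + CV²), the chance that a value exceeds twice baseline is 1 − Φ(ln 2 / (σ√2)).

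- CV 20%: σ = 0.198; 0.693/0.280 = 2.48; chance 0.7%.
- CV 30%: σ = 0.294; 0.693/0.415 = 1.67; chance 4.7%.
- CV 40%: σ = 0.385; 0.693/0.545 = 1.27; chance 10.2%.

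**Many looks.** Looks share a baseline and are not independent. At CV 30%, 1 − (1 − 0.0475)^12 = 44% would be too high. Simulation with a shared baseline gives the following at 12 looks.

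| Subjects | CV | Single visit | Two consecutive visits |
|---|---|---|---|
| Observed baseline >1 g | 20% | 2–3% | 0.1–0.3% |
| | 30% | 11–16% | 1–3% |
| | 40% | 18–28% | 3–7% |
| True level fixed at 1.5–3 g | 20% | about 5% | 0.2–0.5% |
| | 30% | 25–26% | 3–6% |
| | 40% | 42–44% | 8–15% |

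The upper block is lower because some subjects with an observed baseline above 1 g were high by chance, and they rarely double that value later. It is the block that matches the SAP's rule, which sorts subjects by observed baseline.

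**Sensitivity, observed baseline above 1 g.** At CV 30%, the single-visit figure is 3–5% over 2 looks, 10–15% over 10 and 12–18% over 14. At CV 50–60% over 10 looks it is 22–38%, against 4–11% with confirmation. With true proteinuria of 0.8 g or less and CV up to 40%, the excess over 12 looks is about 5% or less.

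Criteria 2 and 3 have the same first-crossing structure. They are not sized here because they also depend on how often the accompanying urine findings are present.

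**The case against.** The case for leaving the plan alone has real weight.

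- **The change is declared.** It is in SAP Table 1 with a reason, and protocol 6.2.1.3 leaves details of supporting endpoints to the analysis plan. A reader might infer an undisclosed contradiction of the protocol; the documents do not support that.
- **The size is assumed.** A reader might infer that noise alone will produce many flares. That does not hold at CV of about 20%, or over about one year at CV of 30% or less. SAP 8.2.8 describes renal flares as relatively uncommon, and if few subjects start above 1 g the total curve may hardly move.
- **The larger percentages describe another group.** The 25–44% results fix the true level at 1.5–3 g. They should not be read as the risk for subjects with observed baseline above 1 g.
- **Twelve looks is long follow-up.** BEL112341 subjects have at most 8 or 10, and Korean sites closed in 2015.
- **Confirmation has its own bias.** A flare treated and resolved within 24 weeks is missed, and investigators may adjust medication freely. In a safety-led study, over-counting may be the cautious choice.
- **The endpoint is descriptive.** It is listed among other efficacy endpoints, with no hypothesis tests. The SAP acknowledges the departure from the parent definition and plans no comparison with it. Proteinuria change and shift tables remain.

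All of this stands, and it limits the point to a missing sensitivity analysis. None of it explains why a confirmed version cannot be shown beside the single-visit one.

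**Conclusion.** The point holds as a modest, inexpensive improvement. The SAP replaces a confirmed flare with a single-visit flare at the same numerical thresholds, and its reason excludes monthly confirmation only. Consecutive Week 24/48 visits with spot ratio and laboratory tests exist throughout follow-up.

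For subjects with observed baseline above 1 g, confirmation would lower the noise-only first-flare percentage by roughly 2 to 3 percentage points at CV 20%, 10 to 13 at CV 30% and 15 to 21 at CV 40% over 12 looks. These figures rest on the assumed CVs, an assumed spread of true proteinuria and no true change. The direction is the same at every CV tried; the effect on the total Safety population curve cannot be stated. No alpha, power or primary conclusion is affected.

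**What to change.** Keep the single-visit analysis as planned and label it *unconfirmed (single visit)*. Add a sensitivity analysis of time to first confirmed renal flare: criteria met at two consecutive Week 24/48 (or Exit) assessments, dated at the first. State whether the same criterion must be met both times, and how a missed assessment between the two is handled.

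Use the same visit grid for every parent group. Do not add the 4-weekly double-blind samples or unscheduled samples; the former would make confirmation easier for subjects who received belimumab in the double-blind phase. Show both versions in Tables 3.23 and 3.24 and Figure 3.12, and report how many subjects met the criteria only at their last assessment. Report also the number with baseline above 1 g, so that readers can judge the scale.

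The cost is a paragraph of SAP text and one further derivation from data already collected. The downside is that flares resolved within 24 weeks, or met only at the last assessment, stay unconfirmed. The confirmed version therefore tends to understate and the single-visit version to overstate, which is why both should be shown.
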